8.3 Secondary outcome statistics

The average baseline demographics for participants in each group will be compared to ascertain that randomisation has indeed led to comparable distribution of participants':

Sex, age, HbA1c level, baseline wound size (cm2), PUSH score, Texas Univ grading score, mobility score, VAS pain score, EQ5-5D-5L score, CWIQ score, duration of wound (weeks), neuropathy status, ischaemia status.

Other clinical parameters will be recorded too, since they are known to be significantly associated with non-healing of DFU: peripheral arterial disease, heart failure, pretibial oedema (Prompers et al, 2008)

To evaluate the wider effects of Granulox treatment on foot ulcer healing compared to the control group, the following parameters will be compared at week 3, 6, 9 and 12 weeks:

- PUSH score
- Texas Univ grading score
- Mobility score
- Ankle range of motion
- Visual analogue pain score
- EQ5-5D-5L score
- CWIQ score

To compare the groups, Mann-Whitney U-test will be applied.

Cox proportional hazards regression analysis will be conducted to investigate the role of Granulox and other covariates (as mentioned above, including aetiology, diabetes etc) in wound healing rates.

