4.2 Secondary objective

 To assess any changes observed in clinical assessments, safety of Granulox, and patient-reported outcomes related to foot ulcers (including pain, mobility, quality of life)

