5.4 Recruitment

Participants will be randomised to either the control group (TaU) or the intervention group (TaU plus administration of Granulox spray) for 12 weeks or until ulcer healing has been achieved. All participants will have demographic data obtained and the following base line measures (table 2):

- Foot ulcer size measured with Convatec grid tool or equivalent measuring tool
- PUSH score (size and characteristics)
- Texas University grading scores.
- Mobility score (LifeSpace questionnaire)
- Quality of life assessment using
 - o EQ-5D-5L
 - o Cardiff Wound Impact Questionnaire
 - VAS pain scale

Table 3. Overview of measurements

Weeks	-2	0	3	6*	9*	12#	18#
· Ulcar size (Converted grid))	X	Х	X	X	X	X	110-11
PUSH score	Χ	Χ	Χ	Χ	X	Χ	A48.400401-144.1
Tiexas Universading score	X	1X	X	: X	\mathbf{X}_{i}	X	
Wound healed status		Χ	Χ	Х	X	Χ	Χ
Lifte Space Questilonnaire		X		X -		X 14 3	
QoL EQ-5D-5L		Χ		Χ	The state of the s	Χ	
QoL CWIQ ************************************	Angel bir sho	1 X 1	orași d	14X1		· XD a	
VAS pain scale	X	Χ	Χ	Χ	Χ	Χ	
Patient experience questionnaire	richt sach Richer Ha d	26021	dylast.	Brutta.		X [®]	

^{*} Allowed to be up to 1 week early or late

[#] Allowed to be up to 2 weeks early or late

@Granulox arm participants only

The Pressure Ulcer Scale for Healing (PUSH) tool, see Appendix 1 is a standardised method of assessing and monitoring the severity and healing of both pressure ulcers and venous leg ulcers (Stotts et al, 2001; Ratliff & Rodeheaver 2005). The Pressure Ulcer Scale for Healing (PUSH) is a valid, responsive, evaluative tool to monitor and document wound progress of foot ulcers (Hon, 2010). Findings also suggest that total PUSH scores predict time-to-heal for foot ulcers (Gardner 2011).

A mobility measure will be taken using a life space questionnaire, see Appendix 1 (Stalvey *et al* 1999). This is a tool that has demonstrated reliability and construct and criterion validity in establishing the spatial extent of an older person's mobility within their home setting. There are other versions (Peel *et al* 2005) that additionally measure the use of aids and equipment however this is not of particular interest within the study, hence the simpler version will be used.

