5.6.2 Secondary outcome measures

This study also aims to record wound characteristics and patient-related outcomes measures, as well as safety endpoints.

- Size and characteristics of foot ulcer, determined with PUSH score (week -2, 0, 3, 6, 9, 12)
- Grading of foot ulcer, using Texas Univ grading score (week -2, 0, 3, 6, 9, 12).
- Wound closure status (week 0, 3, 6, 9, 12)
- Mobility score, as determined by LifeSpace questionnaire (week 0, 6, 12)

- Visual Analogue Pain score (week -2, 0, 3, 6, 9, 12)
- Quality of life score, determined with EQ5D-5L and Charing Cross Venous Ulcer Questionnaire (week 0, 6, 12)
- Wound status check [healed, not healed, recurrence] and any incidences of adverse events (week 18)
- Patient withdrawal rates due to change in management (e.g. need for surgery)
- Wound infection rates, any other adverse events
- Patient experience and satisfaction with the Granulox product and treatment regime

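### Section 8.3 compares PUSH, pain, mobility and quality-of-life scores by an unadjusted Mann-Whitney test; adjusting for the week-0 scores already collected would give more precision at almost no cost

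*Protocol*

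**What the plan says.** Section 8.3 of the protocol lists PUSH, Texas grade, mobility, ankle range of motion, VAS pain, EQ-5D-5L and CWIQ and states that "the following parameters will be compared at week 3, 6, 9 and 12 weeks". The method is one sentence: "To compare the groups, Mann-Whitney U-test will be applied". It names no change score, covariate or stratum.

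The week-0 scores exist. Section 5.4 says "All participants will have demographic data obtained and the following base line measures", and the list that follows includes all five measures at issue here. Section 5.6.2 gives PUSH as "determined with PUSH score (week -2, 0, 3, 6, 9, 12" and pain as "Visual Analogue Pain score (week -2, 0, 3, 6, 9, 12". In Table 3, LifeSpace, EQ-5D-5L and CWIQ are recorded at weeks 0, 6 and 12.

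For these scores, the use that 8.3 states for the week-0 values is a comparability check: "The average baseline demographics for participants in each group will be compared to ascertain that randomisation has indeed led to comparable distribution". The one model with covariates in that section is for wound healing: "Cox proportional hazards regression analysis will be conducted to investigate the role of Granulox and other covariates". Baseline scores might enter that model, but its outcome is not pain, mobility, quality of life or PUSH.

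Section 4.2 words the secondary objective in terms of change: "To assess any changes observed in clinical assessments, safety of Granulox, and patient-reported outcomes related to foot ulcers".

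**The concern.** A patient's pain, mobility, quality-of-life or PUSH score at follow-up depends in part on the same patient's score at entry. A two-sample test on the follow-up score treats that predictable part as noise. Two things follow in a trial of 60 patients. Power is lower than the collected data allow. And if one arm happens to start with, say, less pain, a share of that head start equal to the baseline-to-follow-up correlation shows up as a difference between arms at follow-up. These comparisons carry the trial's patient-reported evidence, so it is worth asking how large either effect is.

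**Working it through.** **Is the comparison really unadjusted?** Section 8.2 takes a difference between time points for ulcer size before applying the Mann-Whitney test. Section 8.3 uses nearly the same test sentence without that step. The authors state a difference when they mean one, so the plain reading of 8.3 is a comparison of the follow-up scores themselves. That is an inference from silence, but 8.3 does fix the test and names no baseline term.

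**Inputs**
- From the protocol: 60 patients, 1:1 allocation, 20% attrition (6.1 and synopsis), two-sided 5% (6.1). Patients per arm: 60 × 0.8 / 2 = 24. With no attrition it is 30.
- Not in the protocol, so assumed: baseline-to-follow-up correlation rho of 0.3, 0.5 and 0.7; effects of 0.6 and 0.8 SD; bivariate normal scores.
- The protocol states no power for these outcomes, so there is no figure of its own to reproduce.

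**Precision.** Adjustment multiplies the residual variance by 1 − rho²:
- rho 0.3: 1 − 0.09 = 0.91; 24 per arm unadjusted is worth 24 × 0.91 = 21.8 per arm adjusted
- rho 0.5: 1 − 0.25 = 0.75; 24 × 0.75 = 18.0
- rho 0.7: 1 − 0.49 = 0.51; 24 × 0.51 = 12.2

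**Power by simulation, 24 per arm.** Mann-Whitney on the follow-up score against Quade's rank analysis of covariance on the week-0 score:

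| Effect | Mann-Whitney | Adjusted, rho 0.3 | rho 0.5 | rho 0.7 |
|---|---|---|---|---|
| 0.6 SD | about 50% | 53–55% | 60–62% | 75% |
| 0.8 SD | about 75% | 77–78% | 84% | 93–94% |

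The gain is about 2 to 4 points at rho 0.3, 9 to 11 at rho 0.5 and 19 to 25 at rho 0.7. With no effect, both methods reject in about 5% of trials. With 30 per arm, a 0.74 SD effect and ordinary analysis of covariance, power goes from about 78% to 83%, 89% and 97–98%, so the pattern does not depend on the attrition figure.

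**Would a change score do instead?** At 24 per arm and 0.83 SD, a Mann-Whitney test on change has 63.5% power at rho 0.3, against 78% for the follow-up score. At rho 0.5 the two are equal (about 78%). At rho 0.7 change has 94%, against 97% for analysis of covariance. Adjustment is the better choice at every value.

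**Carry-over of chance imbalance, 24 per arm.** The SD of the chance baseline difference is √(2/24) = 0.289 SD units.
- P(|difference| > 0.4) = 2 × [1 − Φ(0.4/0.289)] = 0.166
- P(|difference| > 0.6) = 2 × [1 − Φ(0.6/0.289)] = 0.038

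False-positive rate with no treatment effect, given the imbalance (rho 0.5 to 0.7):

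| Baseline difference | Exceeded in | Mann-Whitney | Adjusted |
|---|---|---|---|
| 0.3 SD | about 30% of trials | 4–5% | about 5% |
| 0.4 SD | about 17% | 7–8% | about 5% |
| 0.6 SD | about 4% | 13–21% | about 4% |

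**The case against.** The strongest case on the other side is that nothing here is wrong. Randomisation makes the unadjusted comparison unbiased, and its type I error is about 5%. That stands, and it rules out two stronger readings.

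A reader might infer that the test cannot answer an objective about change. It can: over randomisation the expected between-arm difference at follow-up equals the expected between-arm difference in change.

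A reader might also infer that false-positive rates of 13 to 21% are a general property of the plan. They belong to a 0.6 SD imbalance, which is exceeded in about 4% of trials for any one measure. At 0.4 SD the rate is 7 to 8%, and at 0.3 SD there is no inflation.

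Other points also stand in part. The power gains rest on correlations and effects that the protocol does not give, and at rho 0.3 they are small. The simulation uses normal scores, whereas PUSH falls to 0 at closure and LifeSpace is seven yes/no items; floors and ties may change the gains. Stratification at PUSH 5/6 (6.1.1) limits imbalance in PUSH, though not directly in pain, mobility or quality of life.

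That the form of the analysis variable might be settled in a statistical analysis plan carries less weight, because the protocol already names the test. If change or adjustment was intended, 8.3 does not say so.

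**Conclusion.** The point holds as one of efficiency. As written, 8.3 compares five secondary measures without the week-0 scores that the trial collects for each. The cost is precision: negligible if baseline and follow-up are weakly correlated, and about 9 to 25 power points for rho between 0.5 and 0.7, under normal scores, 24 per arm and effects of 0.6 to 0.8 SD. In an unlucky trial, chance imbalance can also carry into the result, noticeably only when it is large. The documents do not support calling the planned test invalid or biased, and the primary outcome and sample size are untouched. It is a free improvement for secondary outcomes.

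**What to change.** In 8.3, state that PUSH, VAS pain, LifeSpace, EQ-5D-5L and CWIQ, at each visit at which they are collected (LifeSpace, EQ-5D-5L and CWIQ at weeks 6 and 12 only), will be compared between arms by analysis of covariance. The covariates are the week-0 score of the same measure and the stratification factors (diabetes yes/no, PUSH category). Report the adjusted mean difference with its 95% CI. Name a rank analysis of covariance (Quade) as the rank-based test; it is needed alongside the model because on its own it supplies no adjusted difference or interval.

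Keep the Mann-Whitney test for Texas grade and ankle range of motion, so that neither loses its named test, and as a sensitivity analysis for the other five measures.

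The cost is a few lines in 8.3, slightly more analysis work and a simple rule for a missing week-0 score, for example mean imputation that ignores arm. No new data, visits or patients are needed.

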HAWS; Haemoglobin Application to Wounds Study, a single-centre, controlled, prospective randomized trial

Version 6, dd 10July 2018

Chief Investigator's Statement of Ownership and Content.

I, [name], confirm that this protocol is my work and is owned by me. The protocol conforms with standards outlined in the Declaration of Helsinki 1964.

Name (PRINT): [name]

Signature:

Date: LATH SEP. 2018

RESEARCH PROTOCOL SUMMARY

TITLE:	Haemoglobin Application to Wounds Study, a single-centre, controlled, prospective, randomized trial of Granulox
	haemoglobin spray for adjuvant treatment of foot ulcers
Short title:	HAWS; Haemoglobin Application to Wounds Study
IRAS number	227421
Device description	Granulox® Medical device. Class III, CE 0482
	Indications: Granulox® is a spray for use on chronic wounds. Granulox® is an innovative medical device for the proposed treatment of chronic wounds, such as venous leg ulcer, arterial leg ulcer, mixed leg ulcer, foot ulcers, secondary healing of surgical wounds and pressure sores. Granulox® can also be used on sloughy and infected wounds. Each canister contains 12 ml of spray, sufficient for 30 wound treatments.
Study design	Single-centre, controlled, prospective randomized trial
Primary objective	To determine the efficacy of the Granulox spray as an adjuvant therapy for foot ulcers at 3, 6, 9 and 12 weeks post-baseline - Healing rate (ulcer size; 12 weeks is endpoint for power calculation), as measured with surface area scoring grid
Secondary objectives	Clinical assessment at -2, 0, 3, 6, 9 and 12 weeks, and - PUSH ulcer size/grading score - Texas Univ grading score - Wound closure Safety of Granulox spray throughout trial duration, up to 12 weeks - Wound infection incidence; secondary interventions Patient-reported outcome measures at 0, 6 and 12 weeks - Patient mobility score (LifeSpace questionnaire) - Quality of life score (EQ-5D-5L and CWIQ) - Visual Analogue Score for pain associated with DFU Status of wound at week 18 - Healed, not healed, recurrence.
Patient population	A total of 60 participants, over the age of eighteen, with measurable foot ulcer, treated in clinic. Forty patients to have a DFU and further 20 patients to have nondiabetes related foot

	Indiana B. III in the second s
	ulcer. Participants must have the capacity to provide informed written consent and complete patient reported outcome measures.

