To further illustrate the point concerning the impact of foot ulcers: the healing rate of DFUs is poor; on average, 24% of wounds have healed by week 12 of treatment, and only 31% at 20 weeks of treatment (Margolis, 1999). A cohort study involving 31 diabetic patients determined that the average healing time for neuropathic DFUs is 78 days whereas this increases to 133 days for patients with additional peripheral vascular disease (Zimny et al, 2002). Further analysis has shown that the size of the ulcer negatively correlates to the healing rate, whereas a patient's age, sex, or type of diabetes is not associated with a change in healing rate outcome (Oyibo, 2001). DFU healing progress at 4 weeks of treatment is a predictor of the likelihood that the wound will be healed by 12 weeks of treatment. If the wound has not healed by at least 50% after 4 weeks, the likelihood that the DFU will be completely healed by 12 weeks is reduced to circa 10% (Sheehan, 2003). Taken together, there is a major group of patients with DFU -those with larger ulcers, and co-morbidities, responding poorly to standard treatment in the first 4 weeks – that is at risk of ending up with long-term wounds taking over 3 months to heal, if at all.

Oxygen is an essential component of the wound healing process (Hunt et al, 1969). Poor circulation due to diabetic angiopathy impairs the healing process and limits the degree of required growth factor release and angiogenesis (Falanga, 2005; Mathieu et al, 2006). Increasing oxygen levels can be achieved in various ways, including hyperbaric chamber treatment (Faglia, 1996). However, this method is costly, cumbersome and logistically challenging. A novel haemoglobin spray that is designed to enhance wound healing, including non-diabetic foot ulcers and DFUs, by enriching the wound area with oxygen using porcine haemoglobin is now available in the UK. The product is called Granulox and it marketed by InFirst Healthcare Ltd. The mode of action is the application of porcine haemoglobin onto a wound to facilitate increase oxygen levels through diffusion into the wound area (Arenberger et al, 2011; Norris, 2014; Hunt & Elg, 2016). Hunt & Elg, in a study with retrospective analysis of standard care DFUs and prospective assessment of Granulox adjunct therapy DFUs, have shown that the healing rate for chronic wounds is much accelerated with haemoglobin treatment. Figure 1 summarises their data.

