6. SUBJECTS

6.1 Anticipated number of research subjects

There is pilot data to base a *priori* sample size calculation on, but this concerns a single retrospective study (Hunt and Elg, 2016). In their study, they observed 37% (control) and 89% (Granulox) wound size change versus baseline measurement at 12 weeks. This would mean that 14 patients (7 in each arm) would be sufficient to have the trial powered to 80%. For this present trial, a more conservative approach is taken, see Table 4. The earlier published average healing rate of 25% is used as the anticipated minimum healing rate (Margolis, 1999). Since some patients may require surgical intervention or may withdraw, a hypothetical 20% dropout rate is calculated into the sample size (actual attrition rate is a study objective). A theoretical 1:1 allocation to the control and Granulox intervention group respectively will be applied. However, because the PUSH score is not known beforehand this may not be achieved if more patients are recruited into one of the two PUSH cohorts. Diabetic foot ulcers (DFUs) and other foot ulcers will be randomised from separate randomisation lists.

The primary outcome, average percentage decrease in ulcer size between baseline and 12 week follow-up is used for sample size calculation. Power calculations for sample size, 80% power and 5% significance, based on two-sided Mann-Whitney U-test. A priori power calculations using GPower 3.1 software, result in the following sample size summarized in Table 4. This is based on the DFU study by Hunt and Elg. A further 20 patients with non-diabetic foot ulcers will be recruited to pilot what impact Granulox has on those types of wounds.

Table 4, Sample size calculation

	Median change in DFU ulcer size at 12 weeks (presume decrease for both arms, ie one-tailed approach)	Standard Deviation
Arm A (hypothetical)	52%	30%
Arm B (hypothetical)	25%	30%
	Power beta of 80%, Alpha p-value of Sample size required without any dro	

Sample size with 20% attrition rate included: 40

Total of 40 DFU patients:

- 20 Patients to receive treatment as usual (TaU)
- 20 Patient to receive TaU plus Granulox spray

Plus 20 non-DFU foot ulcers:

- 10 Patients to receive treatment as usual (TaU)
- 10 Patient to receive TaU plus Granulox spray

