8. STATISTICAL CONSIDERATION AND DATA ANALYSIS PLAN

8.1 Analysis of baseline characteristics

To determine the demographics and characteristics of the patients in the two arms the following data will be collated:

- Age
- Gender
- BMI
- Smoking status
- Significant comorbidities, including peripheral arterial disease, heart failure, pretibial oedema.
- Aetiology and location of wound
- Presence of diabetes, and if so length of having condition
- Neuropathy
- Offloading of the foot ulcer
- Ankle-Brachial Index value (measured within last 3 months)
- Wound infection or not (or infected at any stage of participation)

Any differences in distribution will be established with Chi-squared test or ANOVA as indicated.

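### The Cox model in Protocol section 8.3 has an open list of 18 or more covariates for perhaps 14 closures, and the baseline list it may draw on includes infection after randomisation

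*Protocol*

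**What the plan says.** Section 8 of the protocol is titled as a data analysis plan. Its last analysis, in section 8.3, reads: "Cox proportional hazards regression analysis will be conducted to investigate the role of Granulox and other covariates (as mentioned above, including aetiology, diabetes etc". The modelled outcome is given only as wound healing rates. No event is defined, and the list has no limit, selection rule or order of entry.

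Two lists stand above that sentence in 8.3. The first is introduced as a check that randomisation balanced the arms. It begins "Sex, age, HbA1c level, baseline wound size (cm2), PUSH score, Texas Univ grading score, mobility score, VAS pain score, EQ5-5D-5L score, CWIQ score" and goes on to wound duration, neuropathy and ischaemia. The second is recorded because "they are known to be significantly associated with non-healing of DFU: peripheral arterial disease, heart failure, pretibial oedema".

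The two covariates named as examples, aetiology and diabetes, are in neither list. Both are in section 8.1, among the baseline characteristics. That list ends with "Wound infection or not (or infected at any stage of participation"). Section 5.6.2 lists wound infection rates as a secondary outcome.

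The protocol summary gives the trial size as "A total of 60 participants", 30 per arm. For diabetic foot ulcers under standard treatment, the Introduction says that "on average, 24% of wounds have healed by week 12 of treatment". The protocol does not state how many closures it expects in this trial.

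**The concern.** A Cox model draws its information from events, not patients. With about one closure per covariate or fewer, the partial likelihood may have no finite maximum. Where an estimate exists, it tends to lie too far from a hazard ratio of 1, and its Wald test rejects too often.

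This matters for three reasons. Wound closure is a secondary outcome (section 5.6.2), yet it is missing from the parameters that 8.3 compares by Mann-Whitney test, so the Cox model is the only stated comparison of arms that can address it. The trial is unblinded (section 6.1.1), so an open list leaves room to choose covariates after results are seen. And if infection during the study enters the model, the Granulox hazard ratio is adjusted for something that treatment may affect.

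**Working it through.** The protocol has no event or covariate count for this model to reproduce. The steps below use its lists and cited rates.

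**1. Covariates.** Section 8.3, first list: 13. Second list: 3. Named examples from 8.1, aetiology and diabetes: 2. Total 13 + 3 + 2 = 18. The other items of 8.1 are BMI, smoking, wound location, diabetes duration, offloading, ankle-brachial index and infection: 7 more, so 25. Splitting factors with several levels would add terms. Some variables overlap: PUSH includes an area sub-score, and ischaemia status overlaps with peripheral arterial disease. The Texas grade does not duplicate area; it scores depth, infection and ischaemia (Appendix 1).

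**2. Closures.** Expected closures = number of patients × proportion closed. The 24%, the 31% at 20 weeks and the roughly 10% for slow healers come from the Introduction; the 20% attrition comes from section 6.1. The hazard ratios are assumptions.

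| Assumption | Calculation | Closures | Per covariate (18) |
|---|---|---|---|
| 24% in both arms | 0.24 × 60 | 14.4 | 0.80 |
| 24%, 20% attrition | 0.24 × 48 | 11.5 | 0.64 |
| 10%, with and without attrition | 0.10 × 48 to 0.10 × 60 | 4.8 to 6.0 | 0.27 to 0.33 |
| 31%, with and without attrition | 0.31 × 48 to 0.31 × 60 | 14.9 to 18.6 | 0.83 to 1.03 |
| 24% control, hazard ratio 2 | 7.2 + 30 × (1 − 0.76²) | 19.9 | 1.11 |
| 24% control, hazard ratio 3 | 7.2 + 30 × (1 − 0.76³) | 24.0 | 1.33 |

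The range is about 5 to 24 closures. With 25 covariates, 14.4 closures give 14.4/25 = 0.58 each.

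**3. Joint model, simulated.** Three separate simulations used 60 patients, no treatment or covariate effects and about 14.4 expected closures. The first two recorded closure at 3-weekly visits and used Efron ties, with 900 and 600 trials. Small models had two covariates, or treatment plus the two stratification factors (marked *).

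| Under no effect | 18 covariates | Small model |
|---|---|---|
| No usable fit | 8.9%; 57/600 = 9.5%; about 12% | about 0% |
| Granulox test rejects at 5% | 11.7%; 11.6%; about 9% | 3.6%; 6.0%*; about 3% |
| Hazard ratio above 4 or below 0.25 | 28.4%; about 26% | 2.1%; 2.5% |
| Central 90% of hazard ratios | 0.06 to 12.1 | 0.34 to 2.69* |

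More events do not cure the test: with 18 covariates it still rejects in 12.3% at 20.9 events, 10.8% at 22 and about 13% at 24. The spread does narrow, to 14.7% extreme hazard ratios at 20.9 events. At a true hazard ratio of 2 (19.7 events), the median estimate is 3.05, against 2.03 with two covariates. With 25 covariates, 354 of 600 fits (59%) failed. Event counts below 14 were not simulated, but they leave fewer events per covariate.

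**4. Infection.** Infection that begins after week 0 cannot describe the arms at randomisation, yet 8.1 would compare it between arms as a baseline difference. As a fixed Cox covariate it would also treat later infection as known from week 0, although a patient whose wound closes early has less time to become infected.

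**5. What a small model can do.** Treatment plus two stratification factors is three parameters: 14.4/3 = 4.8 events each. By Schoenfeld's formula, power for a hazard ratio of 2 at 14 events is Φ(√(14/4) × 0.693 − 1.96) = Φ(−0.66), about 25%. For 80% power the events needed are 4 × (1.96 + 0.842)²/0.693² ≈ 65.3, so 66.

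**The case against.** A reader might infer that the protocol fixes a model with at least 18 terms, infection among them, on 14 events. The text does not say so. It names no joint model, and fitting covariates one at a time or selecting a few would fit its wording. The 13 variables of the first list are introduced as a balance check, not as Cox covariates. A statistical analysis plan, not shown here, may settle the selection. This stands: the results in step 3 are conditional on joint entry.

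The infection point is also partly inference. If the reference back stops at the lists in 8.3 plus the two named examples, the count is 18 and infection is not among them. Infection enters only on the wider reading, where the count is about 25. That reading is plausible because both named examples come from 8.1, but it is not stated. Nor is it documented that treatment affects infection.

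The 14 closures are not a protocol figure. They carry a rate for diabetic ulcers under standard treatment over to both arms and to the 20 non-diabetic patients. Attrition and the exclusion of fast healers after the two-week run-in lower the number; any benefit and the week 18 check raise it. The event itself is assumed too, since section 8.2 uses healing rate for traced ulcer size.

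What these objections leave is an open covariate list stated in the protocol's own analysis section, and a partly post-randomisation variable placed under baseline characteristics. The second needs correcting whatever the Cox model contains.

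**Conclusion.** The point holds in limited form. The protocol gives an unbounded covariate list that its own lists fill with 18 variables, or about 25, for roughly 5 to 24 closures: about 0.3 to 1.3 per covariate with 18. Entered jointly, these would make the Granulox hazard ratio unstable and its test anti-conservative at every event count simulated, from about 14 to 24. The documents do not support the stronger claim that such a model is already fixed, or that it certainly adjusts for infection.

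The listing of later infection as a baseline characteristic is an error as written. The effect on the trial is moderate: this is a secondary analysis, and the Mann-Whitney comparison of ulcer size at week 12 is not affected. The size rests on joint entry, on closure being the event, and on the assumed healing rates.

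**What to change.** In section 8.3, replace the open list with a closed model, for example: *Time to wound closure will be analysed by a Cox model with treatment and the randomisation stratification factors, diabetes and baseline ulcer size. Because closure is recorded at 3-weekly visits, ties will be handled by Efron's method or a discrete-time model will be used. Other baseline factors will be examined one at a time, descriptively.* Before the analysis, state whether ulcer size enters as the PUSH stratum or as log week-0 area. Entering diabetes as a covariate rather than a stratum keeps an estimate for a factor that 8.3 names.

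In section 8.1, limit infection to status at week 0, and report later infection only as an outcome by arm.

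The change is to analysis wording only and needs no new data. It gives up a multivariable prognostic model, which 60 patients cannot support. The hazard ratio remains imprecise, so it should be reported as exploratory with its confidence interval. If closures fall near the low end of the range, even three parameters have only 4.8/3 = 1.6 events each, a setting not simulated here.
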